6.2.6. Full 24 Month Analyses

In general, the same analysis approach for the changes from baseline GA lesion size for the final reporting of the full 24 months will be repeated as described in Sections 6.2.2, 6.2.3, 6.2.4, 6.2.5. Key differences include:

- The definition of excessive missed/not received injection in the supplementary estimand will be defined based on the Month 24 period. The threshold for missed/not received injections due to the COVID-19 pandemic is missing 4 or more injections for the Monthly schedule group and 2 or more injections for the EOM schedule group prior to the Month 24 visit attributable due to the COVID-19 pandemic.
- The Month 12 PP set will be replaced with the Month 24 PP set for the supplementary analysis.

6.2.7. Exploratory Endpoints Closely Related to the Primary Efficacy Endpoint

Analyses of the following endpoints closely related to the primary efficacy endpoint, will be performed for the mITT set to provide supplemental information.

6.2.7.1. Change in Square Root of GA Area

For each subject and timepoint, the square root of GA area will be calculated. The change from baseline in square root of GA area will be analyzed using the same methodology as described for the primary endpoint analysis in Section 6.2.2, except that change from baseline in the square root of GA area will be the response variable. This analysis will be conducted both for the first 12 months summaries as well as the full 24 months summaries.

6.2.7.2. Percent Change in GA Area and Square Root of GA Area

For each subject and timepoint, the percent change in GA area will be defined as the change from baseline in GA area (mm^2) divided by the GA area (mm^2) at baseline and the percent change in square root of GA area will be defined as the change from baseline in GA area (mm) divided by the GA area (mm) at baseline. The percent change in GA area from baseline and percent change in square root of GA area will be analyzed using the same methodology as described for the primary endpoint analysis in Section 6.2.2, except that percent change from baseline will be the response variable. This analysis will be conducted both for the first 12 months summaries as well as the full 24 months summaries.

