2.2.6. Exploratory Endpoints Closely Related to the Primary Efficacy Endpoint

- Change from baseline in square root of the total area of GA lesion(s) in the study eye (in mm) based on FAF over time.
- Percent change in total area of GA lesion(s) in the study eye (in mm²) based on FAF over time.
- Percent change in square root of the total area of GA lesion(s) in the study eye (in mm) based on FAF over time.

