3.4. Sample Size and Power Considerations

A total of approximately 600 subjects will be randomized in a 2:2:1:1 ratio to receive treatment with PM, PEOM, SM, or SEOM. The annual growth rate in GA lesion area is expected to have a mean of 1.47, 1.70 and 2.13 mm^2/year for PM, PEOM and Sham-Pooled (Sham) groups, respectively, as estimated from the results of a Phase 2 trial of pegcetacoplan. The standard deviation of the lesion growth is estimated to be 1.50 mm^2 based on the same Phase 2 trial data or 1.25 mm^2 based on natural history data (Holekamp N, 2019).

The power of the study for the primary endpoint is presented in Table 1 for sample size of 200 in each treatment arm. The approximation is calculated using PROC POWER ONEWAYANOVA, Statistical Analysis System (SAS) 9.4. The study power for the primary endpoint is likely larger when utilizing the longitudinal data to model the primary endpoint. The actual study power for the primary endpoint may also vary based on the distribution of the stratification factors (i.e., lesion area at screening, presence of CNV in fellow eye). Study power was not calculated for key secondary functional endpoints.

Table 1: Power to Detect a Difference among Three Groups with an Equal Size of 200 Subjects

Common Standard Deviation (mm ²)	Alpha (two-sided)	Power for a true mean of 1.47, 1.70, and 2.13 mm ² /year for PM, PEOM and Sham, respectively		
		PM vs Sham	PEOM vs Sham	Overall (Among 3 groups)
1.25	0.0495	> 99.9%	92.9%	99.9%
1.25	0.0248	99.9%	88.2%	99.7%
1.40	0.0495	99.7%	86.5%	99.3%
1.40	0.0248	99.3%	79.4%	98.6%
1.50	0.0495	99.2%	81.5%	98.4%
1.50	0.0248	98.4%	73.1%	97.0%

PM = pegcetacoplan Monthly, PEOM = pegcetacoplan Every-Other-Month; Sham = Sham Monthly + Sham Every-Other-Month

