4.5. Per-Protocol Sets

The Per-Protocol (PP) sets will be identified separately for Month 12 and Month 24 analysis, respectively (i.e., Month 12 PP set and Month 24 PP set). The PP sets consist of all mITT subjects who have a valid GA lesion area assessment for either Month 10 or 12 (Month 12 PP set) or a valid GA lesion area assessment for at least one of Month 18, 20, 22, 24 (Month 24 PP set) and who follow the protocol without any major deviation(s) that could affect the primary efficacy data.

A valid GA lesion area assessment is defined as a non-missing measured GA lesion area assessment at a given timepoint where at least 75% of the expected injections over the course of participation ahead of the given timepoint have been received by the subject. For example:

- A valid GA lesion measurement at Month 10 in the Monthly arm would be a result available at Month 10 with no more than 2 missed injections prior to the Month 10 assessment (10 scheduled before Month 10, 2 missed = 80% compliance).

- A valid GA lesion measurement at Month 20 in the every other month (EOM) arm would be a result available at Month 20 with no more than 2 missing injections prior to the Month 20 assessment (10 scheduled before Month 20, 2 missed = 80% compliance).

Major protocol deviations (PDVs) that lead to exclusion from the Month 12 PP set and the Month 24 PP set are as follows:

(i) Violations of inclusion and/or exclusion criteria

A PDV with any of the following inclusion and/or exclusion criteria violations will be classified as a major PDV:

Inclusion Criterion #3: Clinical diagnosis of GA of the macula secondary to AMD as determined by the Investigator and confirmed by the Reading Center

Inclusion Criterion #4: The GA lesion must meet the criteria listed in the protocol as determined by the central Reading Center's assessment of FAF

- Total GA area must be ≥ 2.5 and ≤ 17.5 mm² (1 and 7 disk areas [DA] respectively).
- If GA is multifocal, at least one focal lesion must be ≥ 1.25 mm² (0.5 DA), with the overall aggregate area of GA as specified above in 4a.
- The entire GA lesion must be completely visualized on the macula centered image and must be able to be imaged in its entirety and not contiguous with any areas of peripapillary atrophy.
- Presence of any pattern of hyperautofluorescence in the junctional zone of GA. Absence of hyperautofluorescence (i.e., pattern = none) is exclusionary.

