5.2. Demographic and Other Baseline Characteristics

Demographic and baseline characteristics will be tabulated using descriptive statistics by treatment group and overall. Tables will be produced for the following analysis sets: ITT, Safety, mITT, Month 12 PP and Month 24 PP (as appropriate), PK, PD, and Genotyping. The following variables will be included in the tables:

The demographic data are:

- Age at screening (years) and in categories
 - < 65
 - 65-<75
 - 75-<85
 - ≥ 85
- Sex
- Race
- Ethnicity
- Geographic Region (United States vs. Rest of World)
- Country
- Weight (kg) at baseline
- Height (cm) at baseline
- Body Mass Index (kg/m^2)
- Tobacco use status (ever, never)

Baseline characteristics will be summarized for both study eye and fellow eye whenever applicable. Baseline characteristics include:

- Study eye laterality (OD, OS)
- Study eye status (better-seeing eye vs. worse-seeing eye, based on NL-BCVA – in the case of ties, study eye status will be classified as the better-seeing eye)
- GA lesion size (mm^2) (assessed by FAF)
- GA lesion size in categories, determined by reading center (as randomized status and actual status):
 - < 7.5 mm^2
 - $\geq 7.5 \text{ mm}^2$
- GA lesion size categories (approximately tertiles based on APL2-303/304 combined data*) – study eye only
- Square root GA lesion size (mm)

- GA lesion location (subfoveal involvement vs. non-subfoveal involvement) (assessed by FAF)
- GA focality (unifocal vs. multifocal) (assessed by FAF)
- Number of areas of atrophy (none, 1, 2-5, 6-10, 11-20, >20, cannot be determined) (assessed from FAF)
- Presence of double-layer sign (DLS) (assessed by SD-OCT)
- Central subfield thickness (CST) (assessed by SD-OCT)
- Presence of macular neovascularization (MNV) (i.e., subclinical CNV) (assessed by Optical Coherence Tomography Angiography (OCT-A))
- Presence of pseudodrusen (assessed by near-infrared reflectance imaging)
- Number of intermediate/large drusen (0-5, 6-10, 11-20, and >20) (assessed by color fundus photography)
- NL-BCVA in ETDRS letters
- NL-BCVA categories (≥ 70 , ≥ 60 - < 70 , ≥ 35 - < 60 , < 35 ETDRS letters)
- NL-BCVA (< 60 vs. ≥ 60 ETDRS letters)
- LL-BCVA in ETDRS letters
- LL-BCVA categories (approximately tertiles based on APL2-303/304 combined data*) – study eye only
- IOP
- LLD in ETDRS letters
- LLD categories (< 20 vs. ≥ 20 ETDRS letters)
- LLD categories (approximately tertiles based on the APL2-303/304 combined data*) – study eye only

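### SAP 6.2.7.2 leaves the square root out of its formula for percent change in square root of GA area, so the rule taken literally repeats percent change in GA area

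*SAP*

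**What the plan says.** SAP 2.2.6 lists three exploratory endpoints closely related to the primary one. The third is "Percent change in square root of the total area of GA lesion(s) in the study eye (in mm) based on FAF over time".

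SAP 6.2.7.1 covers change on the square-root scale and says that for each subject and timepoint "the square root of GA area will be calculated".

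SAP 6.2.7.2 then gives two definitions in one sentence. For area, "the percent change in GA area will be defined as the change from baseline in GA area" in mm² over baseline GA area in mm². For the square root, "percent change in square root of GA area will be defined as the change from baseline in GA area (mm) divided by" a denominator that is written as "the GA area (mm) at baseline". Both variables go through the repeated-measures model of SAP 6.2.2, for the first 12 months and for the full 24 months.

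No other place supplies the formula. SAP 13.5.1 deals only with combining readers and with indeterminate lesion boundaries. The sample code in Appendix 1.2 does not derive this variable, SAP Section 15 does not mention it, and the protocol's endpoint lists do not contain it.

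**The concern.** The second definition never takes a square root. It divides a change in GA area by a GA area and changes only the unit label, although an area cannot be in mm. The label has no effect on a ratio, so as arithmetic the two definitions are the same.

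Two things could follow. If the sentence is programmed literally, the least-squares means, confidence intervals and p-values reported under the square-root name would be those of percent change in area, and the endpoint in SAP 2.2.6 would not be reported at all. If the programmer corrects it silently, the result is the intended one, but the analysis departs from the written plan without a record.

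**Working it through.** The plan states no numerical result for this endpoint, so there is no figure to reproduce. The check is algebra, followed by an illustration with the plan's own inputs.

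**Inputs**
- Mean annual growth in GA area, from SAP 3.4: "expected to have a mean of 1.47, 1.70 and 2.13" mm²/year for PM, PEOM and pooled sham.
- Eligible baseline area, from the inclusion criterion repeated in SAP 4.5: "Total GA area must be ≥ 2.5 and ≤ 17.5" mm². The randomisation cut of 7.5 mm² serves as a middle value.
- Assumption: each mean growth is applied unchanged at every baseline size, and in year 2 as in year 1.

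**Formulas.** Let A0 be baseline area, A1 area at the visit and g = A1 − A0.
- Literal: (A1 − A0)/A0 = g/A0, which is percent change in area.
- Intended: (√A1 − √A0)/√A0 = √(A1/A0) − 1.
- Since A1 − A0 = (√A1 − √A0)(√A1 + √A0), literal/intended = (√A1 + √A0)/√A0 = 1 + √(A1/A0). This exceeds 2 when the lesion grows and is below 2 when it shrinks.

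**Worked case.** Sham, A0 = 7.5, g = 2.13, A1 = 9.63. Literal: 2.13/7.5 = 28.4%. Intended: √(9.63/7.5) − 1 = 13.3%. Ratio: 2.13.

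**12 months**

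| Arm (g, mm²) | A0 (mm²) | Literal | Intended | Ratio |
|---|---|---|---|---|
| PM (1.47) | 2.5 | 58.8% | 26.02% | 2.26 |
| PM | 7.5 | 19.6% | 9.36% | 2.09 |
| PM | 17.5 | 8.4% | 4.12% | 2.04 |
| PEOM (1.70) | 2.5 | 68.0% | 29.61% | 2.30 |
| PEOM | 7.5 | 22.67% | 10.75% | 2.11 |
| PEOM | 17.5 | 9.71% | 4.74% | 2.05 |
| Sham (2.13) | 2.5 | 85.2% | 36.09% | 2.36 |
| Sham | 7.5 | 28.4% | 13.31% | 2.13 |
| Sham | 17.5 | 12.17% | 5.91% | 2.06 |

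**24 months.** With growth doubled, the ratio runs from 2.08 (PM, 17.5 mm²) to 2.64 (sham, 2.5 mm²). At 7.5 mm² with sham growth it is 2.25 (56.8% against 25.2%).

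**Relative treatment effect.** At 7.5 mm² and 12 months, PM's reduction against sham is (28.4 − 19.6)/28.4 = 31.0% on the literal formula and (13.31 − 9.36)/13.31 = 29.7% on the intended one.

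**The case against.** The strongest reply is that nobody would misread this. The term being defined and the section heading both name the square root. The sentence contrasts mm² with mm, and mm fits only the square-root variable. SAP 6.2.7.1, immediately before, derives that variable and its change from baseline, which is the intended numerator. SAP 2.2.6 and the baseline characteristics in SAP 5.2 also give the square root in mm. To arrive at area over area, a programmer would have to set all of this aside. In addition, SAP 6.2.7 treats these endpoints as supplemental information, and the relative comparison between arms hardly moves.

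Most of this stands, and it limits the point. It does not remove it, because the only operational definition in either document is wrong as written.

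Three stronger inferences are tempting, and the documents do not support them.
- *Every subject's value would be overstated 2.0- to 2.4-fold.* That range holds at mean 12-month growth. The factor depends on each eye's own A1/A0. With the plan's SD of 1.50 mm² and an assumed normal distribution, about 16% of PM subjects (mean 1.47) would show no growth or shrinkage, with a factor of 2 or less. A 2.5 mm² lesion growing by 2.13 + 2 × 1.50 = 5.13 mm² has a factor of 1 + √(7.63/2.5) = 2.75.
- *The slip defeats the purpose of the square-root scale, which is to reduce dependence on baseline size.* Neither document gives a reason for using that scale. In the illustration above, the intended percent change also depends heavily on baseline: between 2.5 and 17.5 mm² with sham growth it varies 6.1-fold (36.09/5.91), against 7.0-fold (85.2/12.17) for the literal one.
- *The same number would appear twice in one table.* The SAP does not say that the two endpoints share a table.

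**Conclusion.** The definition is wrong as written, and the correction is not in dispute. Taken literally, it duplicates percent change in GA area and fails to deliver the endpoint that SAP 2.2.6 lists. The algebraic identity needs no assumptions. The factor of about 2.0 to 2.4 rests on the plan's mean 12-month growth applied uniformly over the eligible baseline range; at 24 months it reaches about 2.6 for the smallest eligible lesions.

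The point is minor. The intent can be recovered from the surrounding text, and the documents give no sign that the variable was or will be programmed wrongly. The endpoint is exploratory and lies outside the hypotheses in SAP 6.2.1 and 6.3.1, so the primary and key secondary conclusions, the alpha control and the sample size are untouched.

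**What to change.** Reword the second half of the sentence in SAP 6.2.7.2 so that percent change in square root of GA area is (square root of GA area at the visit − square root of GA area at baseline) / square root of GA area at baseline, with the square roots in mm.

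The area definition in the same sentence has no multiplication by 100 either. Add it to both definitions or to neither, so that they stay parallel.

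The cost is one SAP sentence and a check that the derivation specification for the analysis dataset uses the same formula. No data collection, model or sample size changes.

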6.3. Analyses of Key Secondary Efficacy Endpoints

The key secondary efficacy endpoints are listed in Section 2.2.2. At the Month 12 reporting, all key secondary efficacy endpoints will be evaluated based on data from baseline to Month 12 (see Section 3.5). For the Month 12 analyses, post-baseline visits, up to and including Month 12, will be included and nominal p-values will be presented. At the time of the final study analysis, all key secondary efficacy endpoints will be evaluated based on data from baseline to Month 24, and formal statistical testing for key secondary endpoints will be performed as described in Section 6.3.1. Unless otherwise specified, all secondary efficacy endpoints will be analyzed for the mITT set.

6.3.1. Type I Error Management

The planned submission of pegcetacoplan in GA consists of 2 studies of very similar design (APL2-303 and APL2-304), each with multiple endpoints. It is planned to control the type I error rate for the primary endpoint hypotheses testing at the level of the individual studies (as described in Section 6.2.1), and at a level of the submission as a whole for the key secondary endpoints hypotheses testing based on pooling APL2-303 and APL2-304. Figure 2 presents the overall hypotheses testing strategy for the APL2-303 and APL2-304 studies.

The primary endpoint hypotheses in the PM vs. Sham and PEOM vs. Sham will be tested in a hierarchical order within a study. If both hypothesis tests for the primary endpoint in both studies are statistically significant, then hypotheses testing will be performed for the key secondary endpoints within the pooled APL2-303/APL2-304 data for hypotheses H_{2a} – H_{4b} and within the APL2-304 study for H_{5a} and H_{5b} at the presented α level. The key secondary efficacy endpoints hypotheses that will be tested in the pooled APL2-303/APL2-304 studies are below:

- H_{2a} There is no difference between PM and Sham regarding mean change from baseline in monocular maximum reading speed (study eye), as assessed by MNRead or Radner Reading Charts at Month 24.

[figure not shown]
- H_{2b} : There is no difference between PEOM and Sham regarding mean change from baseline in monocular maximum reading speed (study eye), as assessed by MNRead or Radner Reading Charts at Month 24.
- H_{3a} : There is no difference between PM and Sham regarding mean change from baseline in mean FRI Index score at Month 24.
- H_{3b} : There is no difference between PEOM and Sham regarding mean change from baseline in mean FRI Index score at Month 24.
- H_{4a} : There is no difference between PM and Sham regarding mean change from baseline in NL-BCVA score at Month 24 (study eye) as assessed by ETDRS chart.
- H_{4b} : There is no difference between PEOM and Sham regarding mean change from baseline in NL-BCVA score at Month 24 (study eye) as assessed by ETDRS chart.

Hypothesis tests will be conducted in the order indicated by the arrows in [Figure 2](#) and will continue as long as all preceding hypotheses are rejected at a given α level. If both the PM vs. Sham and the PEOM vs. Sham comparisons are statistically significant for a given key secondary endpoint, then the α will be allocated equally to the other key secondary hypotheses. At the study-level, the type I error rate (one-sided) is controlled at 0.025 for the primary endpoint hypotheses. In the submission, the type I error rate (one-sided) is controlled at 0.000625 (0.025^2) for the primary endpoint hypotheses and at 0.025 for the key secondary endpoint hypotheses. All hypothesis tests will be adjusted for the number of DMC unmasked reviews prior to the Month 12 analysis.

Type I error will be controlled by the testing procedure via the graphical methods approach ([Bretz 2009](#)). All confidence intervals and p-values will be presented without adjustments.

[figure not shown]
If at least one of the hypothesis tests for the primary endpoint in the APL2-304 study is not statistically significant but both hypothesis tests for the primary endpoint in the APL2-303 study are statistically significant, then any hypothesis testing for the key secondary endpoints will not be rejected at the submission level. Within the APL2-303 study, hypotheses testing for the key secondary endpoints will be tested as shown in [Figure 3](#) and type I error will be controlled using a fixed sequencing approach. All hypotheses tests will be adjusted for the number of DMC unmasked reviews prior to the Month 12 analysis. All confidence intervals and p-values will be presented without adjustments.

Figure 2: APL2-303 and APL2-304 Hypothesis Testing and Type I Error Control

Endpoint data are compared to sham injections in hypotheses testing. Hypotheses can only be tested in sequential order as indicated by arrows. Sequential testing will continue as long as all preceding hypotheses can successfully be rejected at the given alpha level. At the study-level, the Type I error rate (one-sided) is controlled at 0.025 for the primary endpoint hypotheses. In the submission, the Type-I error rate (one-sided) is controlled at 0.000625 (0.025^2) for the primary endpoint hypotheses and at 0.025 for the key secondary endpoints.

Figure 3: APL2-303 Hypothesis Testing and Type I Error Control If There is No α Remaining in APL2-304 to Allow Pooling Secondary Functional Endpoints

Endpoint data are compared to sham injections in hypotheses testing. Hypotheses can only be tested in sequential order as indicated by arrows. Sequential testing will continue as long as all preceding hypotheses can successfully be rejected at the given alpha level. This testing tree will only be used when APL2-304 cannot pass α from the primary endpoint testing to the pooled secondary functional endpoint testing.

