6. EFFICACY ANALYSES

Efficacy analysis including primary, key secondary, secondary, and exploratory analysis will be performed primarily using the mITT set, with subjects grouped according to the treatment assigned at randomization. Available data from all randomized subjects regardless of adherence to the protocol will be included in the efficacy analyses; this includes data from subjects who discontinued study drug early but continued with study assessments. All efficacy data will be listed for the ITT set.

Unless otherwise noted, hypothesis testing and estimation of treatment effects will be performed with a mixed effect model for repeated measure (MMRM) that includes data from all three treatment arms (PM, PEOM, and Sham). The Sham arm will represent the pool of the two sham treatment groups: SM and SEOM (i.e., the two sham arms will be pooled into a single “control” group). All hypothesis tests for efficacy endpoints will be two-sided.

Unless otherwise noted, analysis of efficacy endpoints (primary, key secondary, secondary, and exploratory) in the overall population will be adjusted for the following randomization stratification factors (actual status) and baseline covariates:

For primary efficacy endpoint

- Presence of CNV in the fellow eye (yes; no)
- Baseline GA lesion area ($< 7.5 \text{ mm}^2$ or $\geq 7.5 \text{ mm}^2$)

For key secondary, secondary, and exploratory endpoints

- Presence of CNV in the fellow eye (yes; no)
- Baseline GA lesion area ($< 7.5 \text{ mm}^2$ or $\geq 7.5 \text{ mm}^2$)
- Baseline value of the endpoint

Of note, the randomization stratification factors were assessed at the screening visit. In the event of a change in status in the GA lesion area between the screening visit and the baseline visit (i.e., GA lesion area $< 7.5 \text{ mm}^2$ at screening to $\geq 7.5 \text{ mm}^2$) then the baseline status will be used.

If a statistical model is not directly specified and if necessary, data will be analyzed with the following approaches:

- For continuous endpoints, the MMRM analysis described for the primary endpoint in Section 6.2.2.
- For categorical or ordinal variables, a Cochran Mantel Haenszel (CMH) test with the baseline category status, presence of CNV in the fellow eye (yes or no), and baseline GA lesion area ($< 7.5 \text{ mm}^2$ or $\geq 7.5 \text{ mm}^2$) as stratification factors.

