6.3.2. Main Analyses of Key Secondary Efficacy Endpoints

6.3.2.1. Monocular Maximum Reading Speed

Maximum reading speed will be calculated per MNRead or Radner user manuals, with no adjustment for reading inaccuracy. An additional step to cap resulting reading speed values at a maximum of 300 words per minute will be implemented. Values above 300 words per minute exceed values reported in the literature for adults with no vision impairment for MNRead (Calabrese et al. 2016) or Radner (Radner et al. 2002; Radner and Diendorfer 2014) assessments. Maximum reading speed will be calculated as the mean of the three highest nonzero reading speeds (or two, or one value, as available) (Baskaran et al. 2019; Patel et al. 2011), except when all words per minute are calculated as 0: then the maximum reading speed will be calculated as 0.

Monocular maximum reading speed in the study eye will be summarized and analyzed in a similar fashion as the primary efficacy endpoint using MMRM described in Section 6.2.2. The model will include treatment (PM, PEOM, Sham), presence of CNV in the fellow eye (yes or no), and baseline GA lesion area ($< 7.5 \text{ mm}^2$ or $\geq 7.5 \text{ mm}^2$) as fixed effects; baseline monocular maximum reading speed as well as the chart type (MNRead or Radner) as covariates, time (in months) as a factor; the time \times treatment interaction term as well as the baseline monocular maximum reading speed \times time interaction term.

The observed values for the monocular maximum reading speed will be summarized by treatment group and visit for both the study and the fellow eye. Summaries will present the descriptive statistics for baseline, absolute values and change from baseline data.

The mean change from baseline in the monocular maximum reading speed of the study eye \pm the standard error as well as the LS mean of the change from baseline in the monocular maximum reading speed of the study eye \pm the standard error will be plotted over time by treatment group.

In addition, the categorical changes (improvements of ≥ 20 to <40 , ≥ 40 to <60 , ≥ 60 and minimal/no change (-20 to 20), worsening of ≥ 20 to <40 , ≥ 40 to <60 , ≥ 60) for the study eye will be summarized by treatment group and visit.

The shift from baseline in the monocular maximum reading speed for the study eye categories over time will be presented by treatment group for the following categories:

- < 40 wpm
- 40 to < 80 wpm
- 80 to <160 wpm
- ≥ 160 wpm

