6.3.2.2. Mean FRI Index Score

The mean FRI Index score will be calculated per the scoring algorithm in the FRI Index user's manual.

The mean FRI Index score will be summarized and analyzed in a similar fashion as the primary efficacy endpoint using MMRM described in Section 6.2.2. The model will include treatment

(PM, PEOM, Sham), presence of CNV in the fellow eye (yes or no), and baseline GA lesion area ($< 7.5 \text{ mm}^2$ or $\geq 7.5 \text{ mm}^2$) as fixed effects; baseline mean FRI Index score and baseline study eye status (Better-seeing Eye vs. Worse-seeing Eye) as covariates, time (in months) as a factor; the time \times treatment interaction term as well as the baseline mean FRI Index score \times time interaction term.

The observed values for the mean FRI Index score will be summarized by treatment group and visit. Summaries will present the descriptive statistics for baseline, absolute values and change from baseline data.

The mean change from baseline in the mean FRI Index score \pm the standard error as well as the LS mean of the change from baseline in the mean FRI Index score \pm the standard error will be plotted over time by treatment group.

In addition, the mean FRI Index score will be converted to the FRI Level variable, as per the user manual, ranging from 1 (Unable to do) to 4 (Totally independent). The categorical changes from baseline (improvements (an increase in FRI level), minimal/no change (no change in FRI level), and worsening (decrease in FRI level)) will be summarized by treatment group and visit. The shift from baseline in the FRI level over time will be presented by treatment group.

All FRI data will be listed for the ITT set.

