6.3.2.3. NL-BCVA Score

The mean NL-BCVA score for the study eye will be summarized and analyzed in a similar fashion as the primary efficacy endpoint using MMRM described in Section 6.2.2. The model will include treatment (PM, PEOM, Sham), presence of CNV in the fellow eye (yes or no), and baseline GA lesion area ($< 7.5 \text{ mm}^2$ or $\geq 7.5 \text{ mm}^2$) as fixed effects; baseline NL-BCVA score as a covariate, time (in months) as a factor; the time \times treatment interaction term as well as the baseline NL-BCVA score \times time interaction term. Note, for the second year, only timepoints that were measured for all three treatment groups will be included in the model.

The observed values for the NL-BCVA will be summarized by treatment group and visit for both the study and the fellow eye. Summaries will present the descriptive statistics for baseline, absolute values and change from baseline data.

The mean change from baseline in the NL-BCVA score for the study eye \pm the standard error as well as the LS mean of the change from baseline in the NL-BCVA score for the study eye \pm the standard error will be plotted over time by treatment group.

In addition, the categorical changes (improvements of ≥ 15 , ≥ 10 to < 15 , ≥ 5 to < 10 , and minimal/no change (-4 to 4), worsening of ≥ 5 to < 10 , and ≥ 10 to < 15 and ≥ 15) for the study eye will be summarized by treatment group and visit.

The shift from baseline in the NL-BCVA of the study eye categories (≥ 70 , $\geq 60 - < 70$, $\geq 35 - < 60$, $\geq 20 - < 35$, < 20 ETDRS letters over time will be presented by treatment group and visit. The above-mentioned ETDRS letter thresholds are based on WHO definitions for vision impairment and blindness. WHO criteria were implemented in an attempt to capture the progressive nature of

Geographic Atrophy and the ultimate treatment goal of avoiding successive vision impairment and blindness through application of active treatment (Pegcetacoplan vs. Sham).^[1]

The average NL-BCVA score over the last 3 months for each reporting period (Month 10 - Month 12 for the Month 12 reporting; Month 22 - Month 24 for the Month 24 reporting) will be calculated for each subject who has at least one NL-BCVA assessment in these windows. The observed values for the NL-BCVA and changes from baseline will be summarized by treatment group for the study eye. Summaries will present the descriptive statistics for baseline, absolute values and change from baseline data.

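### The SAP sends the key secondary tests to pooled APL2-303/304 data but specifies no model with a study term; the effect is a slight loss of precision, not type I error inflation

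*SAP*

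**What the plan says.** SAP 6.3 states that at the final analysis "formal statistical testing for key secondary endpoints will be performed as described in Section 6.3.1". Section 6.3.1 then makes the data set conditional. If both primary comparisons are significant in both APL2-303 and APL2-304, "hypotheses testing will be performed for the key secondary endpoints within the pooled APL2-303/APL2-304 data" for H2a to H4b: reading speed, FRI and NL-BCVA, each for PM and PEOM against sham. If APL2-304 fails on a primary comparison and APL2-303 does not, the tests stay within APL2-303 (Figure 3).

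The models are in 6.3.2:

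- **Reading speed (6.3.2.1):** "The model will include treatment (PM, PEOM, Sham), presence of CNV in the fellow eye (yes or no), and baseline GA lesion area", then "baseline monocular maximum reading speed as well as the chart type (MNRead or Radner) as covariates, time (in months) as a factor", with time × treatment and baseline × time.
- **FRI (6.3.2.2):** the same core, with "baseline mean FRI Index score and baseline study eye status (Better-seeing Eye vs. Worse-seeing Eye) as covariates, time (in months) as a factor". The study-eye item here separates better- from worse-seeing eyes; it does not identify the trial.
- **NL-BCVA (6.3.2.3):** the same core, with "baseline NL-BCVA score as a covariate, time (in months) as a factor".

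Section 6 sets the general rule that efficacy analyses "will be adjusted for the following randomization stratification factors (actual status) and baseline covariates", and lists fellow-eye CNV, baseline lesion category and the baseline value of the endpoint. The sample MMRM code in SAP Appendix 1, Section 1.2.1 has no study variable. The subgroup lists in 6.2.5 and 6.3.5 do not include study.

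**The concern.** The SAP's own principle is to adjust for the factors on which randomisation was stratified. In a pool of two separately randomised trials, study is such a factor, and it is the one that defines the pool. Followed as written, the plan adjusts for the strata inside each trial and leaves out the trial itself.

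Two things could follow. Between-study differences in functional decline would stay in the residual, which widens standard errors. And if missing data made the mix of studies differ between arms at Month 24, part of a between-study difference could enter the treatment contrast.

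There is also a prespecification side. These are confirmatory tests at submission level, SAP 3.4 says that power was not calculated for them, and sponsor analysts are unmasked at Month 12 (3.5), when nominal p-values for the same endpoints are produced (6.3). The pooled Month 24 model is better fixed before then than left to be read into the text.

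**Working it through.** **The plan's own figure.** The only power stated is for the primary endpoint (SAP Table 1). With 200 per group, SD 1.50, differences of 0.66 and 0.43 mm² and two-sided alpha 0.0495, a noncentral t with 597 df gives 99.24% and 81.53%, against 99.2% and 81.5% stated. It reproduces, but it does not bear on the pooled functional endpoints.

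**Inputs.**
- Allocation 2:2:1:1, so PM : PEOM : pooled sham = 1:1:1 (SAP 3.2, for APL2-303). Assumed the same for APL2-304.
- 200 per group per study (SAP 3.4 for APL2-303; assumed for APL2-304), so 400 against 400 in the pool.
- Two-sided alpha 0.05 − 4 × 0.0001 = 0.0496 (SAP 6.2.1). Figure 2 is not available, so giving this full level to one pooled test is an assumption.
- A true effect giving 80% power with study in the model: (1.963 + 0.842) × √(2/400) = 0.198 SD.
- D, the between-study difference in change at Month 24 after the listed covariates, in within-study SDs. Not in the documents; the range below is illustrative.

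**Formula.** With two equal studies, omitting study adds ½ × ½ × D² = D²/4 to the residual variance, so the estimated SE is multiplied by s = √(1 + D²/4). The study mix is the same in every arm, so the contrast is unbiased and its true SE does not change. Hence:
- actual type I error = 2[1 − Φ(1.963 s)]
- power = Φ(2.805 − 1.963 s)

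Worked case, D = 0.5: s = √1.0625 = 1.031 and 1.963 × 1.031 = 2.024. Type I error is 2[1 − Φ(2.024)] = 0.0430, and power is Φ(2.805 − 2.024) = 78.3%.

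| D (SD) | Residual variance ratio | Type I error, no study term | Power, no study term |
|---|---|---|---|
| 0 | 1.0000 | 0.0496 | 80.0% |
| 0.1 | 1.0025 | 0.0493 | 79.9% |
| 0.2 | 1.0100 | 0.0485 | 79.7% |
| 0.3 | 1.0225 | 0.0471 | 79.4% |
| 0.5 | 1.0625 | 0.0430 | 78.3% |
| 1.0 | 1.2500 | 0.0282 | 72.9% |

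With study in the model, both figures stay at 0.0496 and 80.0% for every D.

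**Simulation check.** A single-visit comparison with sandwich standard errors, 6,000 replicates, gave these type I errors without / with the study term:
- Balanced, D = 0.2: 0.0515 / 0.0518
- Balanced, D = 0.5: 0.0443 / 0.0505
- Balanced, D = 1.0: 0.0302 / 0.0535
- 190 v 200 in one study and 180 v 200 in the other, D = 0.2: 0.0513 / 0.0515
- Same imbalance, D = 0.5: 0.0458 / 0.0492
- Same imbalance, D = 1.0: 0.0307 / 0.0508

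Monte Carlo standard error is about √(0.05 × 0.95/6000) = 0.003, so the D = 0.2 rows cannot be told apart from nominal, and no row shows inflation caused by the omission.

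**Bias.** For complete cases, bias = (difference between arms in the share of subjects from one study) × D. A 2-point difference gives 0.02 × D: 0.002 SD at D = 0.1, 0.006 at D = 0.3 and 0.010 at D = 0.5, against a standard error of √(2/400) = 0.071 SD.

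**The case against.** The strongest reply is that this is the APL2-303 SAP. The 6.3.2 models also serve the Month 12 report and the Figure 3 fallback, both single-study analyses in which a study term cannot be fitted. Its absence there does not prove that the sponsor means to leave it out of the pool. That stands: a reader might infer a deliberate choice to omit study, and the documents do not support that. What they show is that no other model is given and no separate pooled analysis plan is cited. On either reading, no study term is specified for the pooled tests.

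A reader might also infer that the pooled tests are invalid or the estimates biased. The calculations do not support this. With equal ratios the omission is conservative. The 0.02 × D figure is a complete-case one; the planned MMRM uses earlier visits under missing at random, which would generally reduce it. The SAP describes the two trials as very similar in design, and nothing in it points to a D of 0.5 or more.

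Finally, APL2-303's own Month 24 estimates are planned in 6.3, so half of a by-study display will exist. That is true, but nothing commits the sponsor to showing both studies beside the pooled result.

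**Conclusion.** The point holds as a small, nearly free improvement. The plan tests H2a to H4b in pooled data, specifies no study term, and does not say expressly which model is fitted there. If the 6.3.2 models are used as written, the cost is slightly wide standard errors: under 2 points of power for D up to 0.5, and about 7 points only at D = 1.0, which no passage suggests. Type I error is not inflated, and any bias from differential missingness would be very small.

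This rests on equal allocation ratios and similar size in APL2-304, on an assumed range for D, and on the full 0.0496 being available to a single test. A smaller local alpha would change the figures but not the direction. A different ratio in APL2-304 would make bias a more serious possibility, but nothing in the documents points to one. The point does not arise in the Figure 3 fallback.

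**What to change.** State in SAP 6.3.1 or 6.3.2 that the pooled key secondary MMRMs use the terms in 6.3.2.1 to 6.3.2.3 plus study (303 or 304) and study × time as fixed effects. The interaction is needed because the response is change from baseline and a between-study difference may grow with follow-up; a constant study effect could under-adjust at Month 24. Report the PM and PEOM effects by study beside each pooled estimate.

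The cost is one sentence and a few parameters. Reading speed and FRI have four post-baseline visits (Months 6, 12, 18 and 24), so 1 + 3 = 4 parameters. NL-BCVA has 12 first-year visits and 6 shared second-year visits, so 1 + 17 = 18. The pool would hold about 1,200 subjects if APL2-304 matches APL2-303 in size. No new data are needed, and the single-study models stay as they are.
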